##### **Contact 1 (24 hours Post Treatment +/- 4 hours) In-person, via telephone, Survey Monkey or Google Docs:**

- Subjects will complete the DVPRS and DVPRS Supplemental Questionnaire.
- Subjects will complete the Needle Tolerance Questionnaire.

##### **Contact 2 (7 days Post Treatment +/- 2 days) In-person, via telephone, Survey Monkey or Google Docs:**

- Subjects will complete the DVPRS and DVPRS Supplemental Questionnaire.
- Subjects will complete the Needle Tolerance Questionnaire.

##### **Acupuncture Needles:**

Auricular semi-permanent (ASP gold) needles: will be remain in your ears for 2-8 days and allowed to fall out on their own.

Intradermal (long) needles using J-type No. 1 (.16) x 15mm: remain in place for 15-30 minutes and are removed by a member of the study staff.

Pylonex needles (Pylonex Pink 1.5mm (0.2 x 1.5mm)): that will be remain in your ears for 2-21 days and allowed to fall out on their own.

This study received DoD Survey License Exemption (#14)-Exempt #0033.

## 10.2 Data Collection:

Describe all the data variables, information to be collected, the source of the data, and how the data will be operationally measured.

We will measure pain utilizing the DVPRS just before BFA therapy, 10-15 minutes after, 24 hours and 7 days post-therapy. Needle Tolerance questionnaire will be administered after DVPRS 10-15 minutes after, 24 hours and 7 days post-therapy.

## 10.3 At any point in the study, will you request, use, or access health information in any form, including verbal, hard copy and electronic?

Yes  No

# 11.0

## Statistical/Data Analysis Plan

### 11.1 Statistical Considerations:

List the statistical methods to be used to address the primary and secondary objectives, specific aims, and/or research hypotheses. Explain how missing data and outliers will be handled in the analysis. The analysis plan should be consistent with the study objectives. Include any sub-group analyses (e.g., gender or age group). Specify statistical methods and variables for each analysis. Describe how confounding variables will be controlled in the data analysis

**Outcome Measures:** There are two outcome measures. The effectiveness outcome measure is the Defense and Veterans Pain Rating Scale (DVPRS). The DVPRS [1,2] consists of an 11-point numerical rating scale with 0 indicating no pain and 10 indicating severe pain. It has been confirmed for reliability and validity in measuring both acute and chronic pain, and is currently the standard for pain measurement throughout DoD and VA health systems. The DVPRS demonstrates linear scale qualities allowing parametric methods to be used. There will be four repeated measurements of the DVPRS: pre-acupuncture, post-acupuncture, 24 hours and one week post-therapy. The needle tolerance outcome will be measured using an in-house developed questionnaire. It employs 5-point ordinal scales to evaluate 12 post-therapy experiences or perception encompassing adverse outcomes, inconveniences, and satisfaction. There will be three repeated measurements: post-acupuncture, 24 hours and 1 week post-therapy.

**Missing Data and Outliers:** Outliers will be checked for clerical error. If improperly recorded, the data will be corrected, and, if found to be properly recorded, will be retained. Medians, means and ranges will be calculated and assessed to accommodate extreme observations. Subjects with missing data will be excluded from analysis and the estimated sample size seen below adjusted for this eventuality. Furthermore, an analysis of sample characteristics of retained and dropped subjects will be performed to determine whether bias has been introduced due to exclusion.

**Sub-group Analysis:** Analysis will center on differences between the three needle groups. The three treatment groups will allow inferences to be made as to whether each group is statistically different from one another. Medication is a potential confounder, but will be addressed by standardizing the dosage of analgesics used by all subjects rather than as a variable in a general linear model with the needle group variable.

Null Hypotheses:

H01 — there is no difference in means of the DVPRS between needle groups; and

H02 — there is no difference in means of the DVPRS between repeated measures; and

H03 — there is no difference in the distribution of the tolerance ordinal scales between needle groups.

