##### **Post-Treatment (10-15 minutes Post Treatment) In-person:**

- Subjects will complete the DVPRS and DVPRS Supplemental Questionnaire.
- Subjects will complete the Needle Tolerance Questionnaire.

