## 11.2 Sample Size:

A priori power analysis was performed using the DVPRS variable as described below. The analysis indicates a minimum of 10 subjects in each needle group, for a total sample size of 30, will have a power of 0.44 to detect the minimal clinically important difference at alpha = 0.14. We will be recruiting a total of 39 subjects, which is inclusive of a 30% drop out rate to accommodate those that may be lost to the study or have missing data to achieve a final total of 30 subjects.

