## 11.6 Data Analysis Plan: Complete description: Background, Objectives, Design, Step by Step how the project is going to be done, Data analysis plan:

Sample and needle group means, standard deviations, medians, interquartile ranges (IQR) and ranges will be calculated for interval variables. Frequency distributions will be produced for nominal and ordinal variables.

The null hypotheses H01 and H02 for the DVPRS outcome measure will be tested by a mixed effects repeated measures analysis of variance (rANOVA). In the event a null hypothesis is rejected, contrasts will be used to investigate effects and differences between and within research and time groups. Null hypotheses H03 will be tested with Chi Squared or Fisher's Exact tests. The significance level of multiple comparison tests will be corrected to  $\alpha = .05$  by the Holm method. [6]

[name], Senior Research Biostatistician Subject Matter Expert for Clinical Research Management under contracts OMNI 0004 3-82 and OMNI 0005 3-126, is the statistical consultant supporting this study. Statistical analysis will be performed with R Version 3.5.1. [7]

[6] Holm, S. 1979. A simple sequential rejective multiple test procedure. Scand. J. Statistics, 6: 65-70.

[7] R Core Team. R: A language and environment for statistical computing. R Foundation for Statistical Computing, Vienna, Austria. 2016 URL <http://www.R-project.org/>.

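### Excluding every subject with any missing data discards pain and tolerance answers already collected, and can bias the needle comparison if loss is outcome-related and differs by needle

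*Combined protocol and SAP*

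**What the plan says.** The rule is in the missing-data paragraph of Section 11.1: "Subjects with missing data will be excluded from analysis and the estimated sample size seen below adjusted for this eventuality". The next sentence adds that "an analysis of sample characteristics of retained and dropped subjects will be performed to determine whether bias has been introduced due to exclusion". No section says that partial records are kept, and no imputation or sensitivity analysis is given. Section 11.2 covers the expected exclusions by recruiting 39, a number "inclusive of a 30% drop out rate to accommodate those that may be lost to the study or have missing data", to reach 30.

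Both outcomes are measured repeatedly. For pain, "There will be four repeated measurements of the DVPRS: pre-acupuncture, post-acupuncture, 24 hours and one week post-therapy". Tolerance (12 five-point items) is recorded at the three post-treatment times. The first is in person, 10-15 minutes after treatment (Section 10.1): "Subjects will complete the Needle Tolerance Questionnaire". The 24-hour and 7-day contacts may be in person, by telephone or online.

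Under Section 11.6 the DVPRS hypotheses H01 and H02 "will be tested by a mixed effects repeated measures analysis of variance (rANOVA"). For tolerance, "Null hypotheses H03 will be tested with Chi Squared or Fisher's Exact tests".

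**The concern.** The rule removes a person, not a missing value. A subject who gave baseline, 10-15 minute and 24-hour scores but missed day 7 leaves every analysis, including those at times when the answers were obtained. Neither planned analysis needs this. A mixed model fitted by likelihood can use incomplete records (Section 11.6 names no fitting method), and a Chi-squared or Fisher test at a given time can use whoever answered at that time.

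Two things are at stake. One is waste, in a trial planned around 10 analysed subjects per needle with a stated power of 0.44. The other is selection. The trial is unblinded and wear time differs greatly: the long needles "remain in place for 15-30 minutes and are removed by a member of the study staff", while the other two types stay in for 2-8 or 2-21 days. If people stop responding because of pain or discomfort, and do so more with one needle, removing them removes the experience that H01 and H03 are meant to compare. The direction is not certain, since subjects with good relief may also stop responding.

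**Working it through.** **Inputs from the plan.** 39 recruited, about 13 per arm, 30 analysed (11.2, 11.4); four DVPRS and three tolerance occasions (11.1); DVPRS mean 4.4, SD 2.4, important difference 25% (11.5), so 0.25 × 4.4 = 1.1 points.

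**The plan's own figure.** The stated power of 0.44 at alpha 0.14 reproduces for the between-group test of a repeated-measures ANOVA with f = (1.1/2.4)/2 = 0.229, 3 groups, 4 measurements, and a correlation of 0.5 (assumed; the plan gives none). λ = f² × N × 4/(1 + 3 × 0.5) = 0.0525 × 30 × 1.6 = 2.52 on 2 and 27 df, giving power 0.442. With 39 complete subjects, λ = 3.28 and power is 0.524. Keeping partial records would put power between these values.

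**Data discarded.** A subject missing only day 7 has given 3 DVPRS scores and 2 questionnaires.

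| Pattern of loss | DVPRS scores discarded / collected | Questionnaires discarded / collected |
|---|---|---|
| 9 of 39 miss day 7 only | 27 / (156 − 9) = 27/147 = 18% | 18 / (117 − 9) = 18/108 = 17% |
| 12 of 39 (about 30%) miss day 7 only | 36 / (156 − 12) = 36/144 = 25% | 24 / (117 − 12) = 24/105 = 23% |
| 9 of 39 leave after 10-15 minutes | 18 / (156 − 18) = 18/138 = 13% | 9 / (117 − 18) = 9/99 = 9% |

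Early comparisons at 10 instead of 13 per arm have standard errors √(13/10) = 1.14 times as large. Read strictly, one blank among 4 + 12 × 3 = 40 fields removes a subject. At an assumed independent 1% blank rate per field, 0.99^40 = 67% of subjects would be complete.

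**Bias in H01 (assumed illustration).** No true needle difference; normal scores with mean 4.4, SD 2.4 and correlation 0.5 between any two times; loss after 24 hours follows a logistic model in the 24-hour score with slope 0.2, 0.35 or 0.55 per point (odds ratios 1.2, 1.4, 1.7), with the intercept set to give the stated loss. If *b* is the complete-case bias at 24 hours, the bias at each other time is 0.5*b*, so the four-time average is *b* × (1 + 3 × 0.5)/4 = 0.625*b*. The table gives absolute values. Loss of high scorers makes the arm that loses more look better.

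| Loss | Bias in the four-time average difference (slopes 0.2 / 0.35 / 0.55) | Share of 1.1, lowest to highest |
|---|---|---|
| 30% in one arm, none in the other | 0.206 / 0.333 / 0.456 | 19% to 41% |
| 23% in one arm, none in the other | 0.159 / 0.259 / 0.357 | 14% to 32% |
| 40% versus 15% | 0.169 / 0.265 / 0.354 | 15% to 32% |
| 30% in both, same mechanism | about 0 | about 0% |

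Likelihood estimation on all observed scores has bias of about 0 in every row, because loss depends only on an observed score. If loss depends instead on the unseen day-7 score (30%, one arm), likelihood is still biased: by 0.05 to 0.12 averaged over times and 0.21 to 0.49 at day 7. Complete cases are biased by 0.21 to 0.46 and 0.33 to 0.73 respectively.

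**Bias in H03 (assumed illustration).** Suppose 40% of an arm rate an item poorly at 10-15 minutes, 30% of the arm are later lost, and poor raters have 2, 3 or 5 times the odds of loss. Solving 0.4p₁ + 0.6p₀ = 0.30 for the loss probabilities of poor raters (p₁) and other raters (p₀) gives p₁ = 0.388, 0.439, 0.500. The proportion rated poor among those retained is 0.4(1 − p₁)/0.7 = 35%, 32%, 29%. Using every 10-15 minute answer gives 40%.

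**The case against.** The strongest reply is about size.

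- **Estimand.** The four-time average includes the pre-treatment score, so part of the bias is baseline imbalance created by selection. For change from baseline (30% loss, one arm), the bias is about 0 at 10-15 minutes and day 7, and 0.16 to 0.36 at 24 hours. Averaged over the three post-treatment times it is 0.05 to 0.12, or 5% to 11% of 1.1. This stands as a matter of scale, but H01 is worded as a difference in DVPRS means, so the average is a fair reading.
- **Sampling error.** Under the same assumptions, with 10 per arm, the standard error of the four-time average difference is 2.4 × √0.625 × √(2/10) = 0.85. The largest illustrated bias is about half of that. This also stands.
- **Scenarios.** Loss confined to one arm is extreme: 30% of 13 is about 4 subjects. The 40% versus 15% case, with the third arm also at 15%, gives 13 × 0.70 = 9.1 losses, matching the plan's 9.
- **Evidence.** Section 9.6 says painful ASP needles deter people from returning, but that concerns a second treatment. Here there is one treatment, and follow-up can be remote. Differential loss is therefore a possibility only.
- **Existing safeguards.** Over-recruitment replaces numbers but does not remove selection. The retained-versus-dropped comparison covers sample characteristics in about 9 dropped subjects over three arms, so it can detect little. It also recovers no data.

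The exclusion might be meant separately for each analysis. The text does not say so, and its reference to retained and dropped subjects points the other way.

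**Conclusion.** The concern holds and should be corrected. The waste follows from the rule itself: up to 18% of collected DVPRS scores and 17% of questionnaires at the plan's 9 losses, less if subjects leave earlier and more at a true 30% loss. The bias is conditional. It needs loss that is related to pain or tolerance and that differs by needle. With 40% versus 15% loss it is 0.17 to 0.35 points in the four-time average, assuming SD 2.4, correlation 0.5 and loss driven by the 24-hour score. It is smaller for change from baseline, and about zero if loss acts equally in all arms. Sampling error will be larger than the bias in a trial of this size. The case for changing the rule is that a better analysis needs no extra subjects or visits, and that the pilot is meant to inform a larger trial.

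**What to change.** Replace the exclusion sentence in Section 11.1 with:

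> All randomized subjects are analysed by assigned needle. The DVPRS mixed model is fitted by restricted maximum likelihood to every observed score. H03 is tested at each time with all tolerance responses available at that time.

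In addition:

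- Keep the complete-case analysis as a sensitivity analysis.
- Add a tolerance sensitivity analysis that counts loss attributed to the needle as poor tolerance, and define in advance what poor means on the five-point items.
- Report loss and its reasons by arm and time.
- State which H03 tests the Holm correction in Section 11.6 covers, since 12 items at three times make 36.

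The cost is one paragraph of the plan and a recorded reason for each loss. The DVPRS analysis will then rest on a missing-at-random assumption, which reduces but does not remove bias if loss depends on later scores that were never seen. Day-7 tolerance answers of lost subjects stay missing, which is why the tolerance sensitivity analysis is needed.

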##### **Screening visit:**

- Obtain and document signed Informed Consent document and HIPAA Authorization
- Review past medical history to verify the inclusion/exclusion criteria
- Collect date of birth, age, gender, contact information, DoD ID number, name of standard of care medications (over-the-counter and prescription)
- Women of child bearing potential will be reminded that they only reliable methods of birth control are total abstinence or surgical removal of the uterus. Other methods, such as the use of condoms, a diaphragm or cervical cap, birth control pills, intrauterine device (IUD), or sperm-killing products are not totally effective in preventing pregnancy. They will be asked to alert study staff if they become pregnant or feel that they might be pregnant.

**Randomization:** Subjects will be randomized using a random number generator using simple randomization into 1 of 3 research treatment groups, with approximately 13 subjects in each arm:

Group 1: Auricular semi-permanent (ASP gold) needles

Group 2: Intradermal (long) needles using J-type No. 1 (.16) x 15mm

Group 3: Pylonex Pink 1.5mm (0.2 x 1.5mm)

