## 11.5 Please provide a justification for your sample size

The study is organized as a mixed effects, randomized design with repeated measures. Subject, gender and age are random effects as subjects are presumed to be a random representation of the population of adult male and female patients seeking treatment for this ailment and obtaining similar care at this and other Air Force medical treatment facilities. Time of repeated measure is a fixed effect as the pre- and post-therapy times cannot be generalized to other times. Needle group is a fixed effect as the needle employed cannot be generalized to other needles and conditions.

A priori power was assessed using G\*Power Version 3.1.9.3 using the DVPRS for effect size. [4] DVPRS mean (SD) pain intensity for a broad sample consisting of inpatients and outpatients suffering from acute and chronic pain has been found to be 4.4 (2.4). The minimal clinically important difference of an 11-point pain scale in patients as will be included in this study has been determined to be a 25% percent change in the score. [5] This difference, mean and SD were used for the DVPRS effect size.

A priori power analysis of the DVPRS variable using the statistical method described below indicates 10 subjects in each research group, for a total sample size of 30, will have a power of 0.44 to detect the minimal clinically important difference at alpha = 0.14.

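### The retained-versus-dropped comparison in section 11.1 cannot determine whether exclusions have biased the needle comparison, and the plan has no other safeguard

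*Combined protocol and SAP*

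**What the plan says.** Section 11.1 (Missing Data and Outliers) states: "Subjects with missing data will be excluded from analysis". It then adds that "an analysis of sample characteristics of retained and dropped subjects will be performed to determine whether bias has been introduced due to exclusion". It does not mention needle arm, list the characteristics, name a test or threshold, or say what follows if a difference appears. Sections 11.1 to 11.6 contain no sensitivity analysis for missing data.

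Related text:
- Section 11.1 (Sub-group Analysis) centres the analysis on differences between the three needle groups.
- Section 11.2 asks for "a minimum of 10 subjects in each needle group, for a total sample size of 30", from 39 recruited. Section 10.1 randomises "with approximately 13 subjects in each arm".
- Section 10.1 records age, gender and medication names at screening, and the DVPRS before treatment. The DVPRS and tolerance ratings follow at 10-15 minutes, 24 hours and 7 days.
- Section 11.6 tests the DVPRS with a mixed effects repeated measures ANOVA.

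**The concern.** Complete-case analysis biases a needle contrast when the dropped subjects differ from the retained ones in a different way in different arms. An overall comparison of retained with dropped subjects does not address that question. Opposite patterns in two arms can cancel in it. Loss driven by pain or tolerance after the last rating leaves no trace in recorded characteristics. With so few dropped subjects, a non-significant result says little.

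Loss that depends on the arm is plausible here. The trial is unblinded (9.3), later follow-up may be remote (10.1), and section 9.6 itself links painful ASP needles to patients not coming back. The results are meant to begin ranking the needles and to inform a larger trial (9.3). A null result from this check could be taken as clearing the complete-case findings, which it cannot do.

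**Working it through.** **Inputs.** DVPRS mean 4.4 and SD 2.4 (11.5). The important difference "has been determined to be a 25% percent change in the score" (11.5). 30 analysed of 39 recruited (11.2), about 13 per arm (10.1). Four DVPRS measurements (11.1). The documents give no strength of selection, so those values are assumed below.

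**1. The plan's own figures.** The target is 0.25 × 4.4 = 1.1 points, so d = 1.1/2.4 = 0.458. Section 11.2 says that 30 subjects "will have a power of 0.44 to detect the minimal clinically important difference at alpha = 0.14". Take the between-groups F test with N = 30, 3 groups and m = 4 measurements, and assume f = d/2 = 0.229 and within-subject correlation ρ = 0.5 (neither is stated). Then λ = f²·N·m/(1 + (m − 1)ρ) = 0.229² × 30 × 4/2.5 = 2.52, and power is 0.442. This agrees with 0.44, so 1.1 points is a fair yardstick. The recruitment figure is 30 × 1.3 = 39, which leaves 9 dropped (9/39 = 23%), or 3 per arm if losses are even.

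**2. Power of the check, 30 against 9.** Two-sample t test, two-sided .05, 37 df, noncentrality d·√(30 × 9/39) = 2.63d.

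| True difference (SD) | Power |
|---|---|
| 0.5 | 0.25 |
| 0.8 | 0.54 |
| 1.1 | 0.80 |

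**3. Opposite selection in two arms.** Let g be the dropped-minus-retained gap in pain at one visit: +g in one arm, −g in another and 0 in the third. Losing 3 of 13 moves an arm's retained mean by 3g/13 from the mean of all 13, so the contrast is off by 6g/13. With equal losses the overall gap is the average of the arm gaps, (g − g + 0)/3 = 0.

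| g (points) | Contrast error (points) | Share of 1.1 | Overall gap |
|---|---|---|---|
| 0.5 | 0.23 | 21% | 0 |
| 1.0 | 0.46 | 42% | 0 |
| 1.5 | 0.69 | 63% | 0 |
| 2.0 | 0.92 | 84% | 0 |

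**4. Selection in one arm only.** The error is 3g/13 and the overall gap is g/3. For g = 2 the error is 0.46 points (42%) and the overall gap is 0.67 points, or 0.67/2.4 = 0.28 SD. Power there is below the 0.25 that applies at 0.5 SD.

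**5. The four-visit group effect (H01).** If the 2-point gaps in step 3 exist only at day 7, the error in the group main effect is 0.92/4 = 0.23 points (21%). It is 0.92 only if the gap is the same at all four visits, baseline included, and in that case change from baseline is unaffected.

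**6. When the compared characteristic is not pain itself.** A simulation used 4,000 trials per setting, 13 per arm and 3 excluded per arm, with high-pain subjects leaving one arm, low-pain subjects another, and random loss in the third. At an assumed correlation of 0.5 between characteristic and outcome, moderate selection gave a contrast error of 0.90 to 1.06 points. The overall check was significant in about 5% of trials, its false-positive rate. Over correlations from 0 to 1 and all selection strengths tried, it was significant in 1% to 5%.

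**7. Testing by arm does not solve it.** Three against 10 needs a gap of about 4.4 points for 80% power (normal approximation, two-sided .05). In the moderate settings of step 6, by-arm tests flagged a difference in either selected arm in only about 17% to 19% of trials.

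**The case against.** The strongest reply is that the defect is one of specification. Section 11.1 does not say that the comparison is pooled over arms, and section 11.6 already plans descriptive statistics by needle group. Nor does 11.1 confine the characteristics to screening data: a subject lost before day 7 may already have pain and tolerance ratings from 10-15 minutes or 24 hours, and nothing bars their use. A reader might infer a pooled check on age, gender and medications alone. The text is silent on both points and does not support that inference.

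The size is also open to challenge. Equal and opposite selection in two arms is an assumption, and needle discomfort does not explain why one arm would lose high-pain subjects and another low-pain subjects. The remark in section 9.6 concerns returning for a second treatment, whereas this trial gives one treatment and accepts remote replies. A reader might infer that the contrast will be wrong by most of the target. The documents do not support that either: it is the top of an assumed range, for one visit. Nor is a finding of no difference assured whatever the truth, since power reaches 0.80 at 1.1 SD.

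These points limit the size and the wording. The comparison as written still cannot determine bias in a needle contrast, and making it by arm would leave it weak and unable to see unobserved outcomes.

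**Conclusion.** The point holds as a limit on what the check can establish. The plan shows neither that bias will occur nor how large it would be. Under the assumed patterns, with 3 of 13 lost per arm, the single-visit error runs from 21% to 84% of the 1.1-point target with an overall gap of zero. It is half that if only one arm is selective, in which case the overall gap is not zero. It is 21% in the four-visit group effect when 2-point opposite gaps arise only at day 7. The power figures rest on a 30 against 9 split and a two-sided .05 t test, neither of which the plan specifies for this check. The trial's pilot status tempers the consequences but does not support the claim to determine bias. The plan should be changed. The change is cheap and gives the reader information that the present check cannot.

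**What to change.** In section 11.1:

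1. Replace the clause about determining whether bias was introduced with *to describe exclusions*.
2. Tabulate losses by needle arm, with time of loss, reason, baseline DVPRS, and last observed DVPRS and tolerance ratings.
3. Add a sensitivity analysis that keeps all observed DVPRS values from subjects with incomplete follow-up in the mixed model. Then set missing 24-hour and day-7 scores 1, 2 and 3 points worse than the model prediction, in one arm at a time.
4. Add a matching check for the tolerance items, with missing ratings set to the worst category in one arm at a time.
5. Report whether the needle ranking or any contrast conclusion changes.

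The cost is SAP wording, a few extra tables and one added field for the reason for loss. The other data are already collected.

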##### **Treatment Visit (Day 0) (may be the same day as screening visit):**

- Subjects will complete the Defense and Veterans Pain Rating Scale (DVPRS) and DVPRS Supplemental Questionnaire before treatment.
- Subjects will be prescribed naproxen 220 mg BID (twice a day) #15 as standard of care treatment for pain (unless they refuse or have a contraindication for use)
- Subjects will be given treatment according to their randomization group following the Acupuncture Procedure below: Step 1: Either the left or right ear is chosen for the placement of the needles per provider or patient preference. Step 2: Needles will be placed in the following points on the chosen ear: Cingulate Gyrus, Thalmus, Omega 2, Point Zero, and Shen Men. Step 3: If the patients desires further pain reduction, acupuncture needles will be placed in the same points in the opposite ear. The maximum number of needles in each ear is 5.

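### H01, as worded, averages the pre-treatment DVPRS into the needle comparison, and no hypothesis tests baseline-adjusted post-treatment pain or group by time

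*Combined protocol and SAP*

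**What the plan says.** The effectiveness outcome is the DVPRS. Section 11.1 says: "There will be four repeated measurements of the DVPRS: pre-acupuncture, post-acupuncture, 24 hours and one week post-therapy". Section 10.1 (Treatment Visit) confirms that the first of these precedes needling: "Subjects will complete the Defense and Veterans Pain Rating Scale (DVPRS) and DVPRS Supplemental Questionnaire before treatment".

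Section 11.1 gives three null hypotheses. H01 is "there is no difference in means of the DVPRS between needle groups". H02 concerns differences between the repeated measures, so it is about time only. H03 concerns the tolerance scales, not pain.

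Section 11.6 tests H01 and H02 with one mixed-effects repeated-measures ANOVA. Section 11.5 treats needle group as fixed and describes the time factor this way: "Time of repeated measure is a fixed effect as the pre- and post-therapy times cannot be generalized to other times". After rejection of a null hypothesis, Section 11.6 says "contrasts will be used to investigate effects and differences between and within research and time groups". It does not say which contrasts, at which visits, or whether they are adjusted for baseline.

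Sections 11.2 and 11.5 state that 10 subjects per group "will have a power of 0.44 to detect the minimal clinically important difference at alpha = 0.14".

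**The concern.** The effectiveness question is whether pain after treatment differs between needles. H01 does not ask that. With pre-therapy as one of four levels of the time factor, the group main effect is a difference in four-visit means. Under randomization, the expected difference at the first visit is zero whatever the needles do. Two losses follow:

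- The target difference shrinks by a quarter.
- Between-subject variation that the baseline score could explain stays in the error term.

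No stated hypothesis covers group by time, change from baseline, or baseline-adjusted post-treatment pain. The comparison that answers the question is left to contrasts chosen later. The risk is a missed difference and a choice made after seeing the data. It is not a false-positive problem in the H01 test itself.

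**Working it through.** **Inputs from the documents.** Mean 4.4 and SD 2.4 (11.5). Minimal clinically important difference of 25%, so 0.25 × 4.4 = 1.1 points (11.5). Ten per group, 30 in all; alpha 0.14; power 0.44 (11.2, 11.5). Four DVPRS measurements, one before treatment (11.1).

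**Assumptions.** The documents give no correlation between visits, so I use 0.3, 0.5 and 0.7, under compound symmetry and under AR(1). One arm differs by 1.1 points from the other two at all three post-treatment visits, and there is no true difference at baseline.

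**Step 1: the plan's own figure.** Take f = (1.1/2.4)/2 = 0.229, four measures, correlation 0.5 and the full difference at every visit. The noncentrality is 0.229² × 30 × 4/(1 + 3 × 0.5) = 2.52. On F(2, 27) at alpha 0.14, power is 0.442, matching the stated 0.44. With zero difference at the pre-treatment visit, f is multiplied by 0.75, the noncentrality is 1.42 and power is 0.317. The match does not identify the layout used: three measures with correlation 0.45 give 0.438.

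**Step 2: H01 as written against the adjusted comparison.** With one arm different, the noncentrality is 10 × (2/3) × d²/v.

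- H01 as written: d = 0.75 × 1.1 = 0.825; v is the variance of the four-visit mean; df (2, 27).
- Baseline-adjusted: d = 1.1; v is the variance of the three-visit post-treatment mean minus cov(post mean, baseline)²/var(baseline); df (2, 26).

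Worked case, compound symmetry 0.5:

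- H01 as written: v = 5.76 × (1 + 1.5)/4 = 3.60; noncentrality = 6.667 × 0.6806/3.60 = 1.26; power 0.30.
- Baseline-adjusted: v = 5.76 × (2/3 − 0.25) = 2.40; noncentrality = 6.667 × 1.21/2.40 = 3.36; power 0.53.

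Results at alpha 0.14:

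| Correlation | H01 as written | Baseline-adjusted | Noncentrality ratio |
|---|---|---|---|
| Compound symmetry 0.3 | 0.35 | 0.51 | 1.90 |
| Compound symmetry 0.5 | 0.30 | 0.53 | 2.67 |
| Compound symmetry 0.7 | 0.27 | 0.63 | 4.44 |
| AR(1) 0.3 | 0.39 | 0.49 | 1.48 |
| AR(1) 0.5 | 0.33 | 0.46 | 1.74 |
| AR(1) 0.7 | 0.29 | 0.48 | 2.45 |

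At alpha 0.05, compound symmetry 0.3, 0.5 and 0.7 give 0.18 vs 0.30, 0.14 vs 0.32 and 0.13 vs 0.42.

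**Step 3: simulation.** These runs (10,000 trials per case, alpha 0.14) also pay for estimating the baseline slope. Compound symmetry 0.3, 0.5 and 0.7 give 0.34 vs 0.49, 0.29 vs 0.51 and 0.27 vs 0.62. AR(1) 0.5 and 0.7 give 0.33 vs 0.44 and 0.28 vs 0.47. With no needle effect, rejection is 0.138 and 0.143, so neither test inflates error.

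**Step 4: a shorter-lived effect.** If the difference has gone by day 7, power at alpha 0.14 and correlation 0.5 is 0.211 vs 0.325 (compound symmetry) or 0.226 vs 0.288 (AR(1)).

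**Step 5: is the omnibus interaction a substitute?** Under compound symmetry its noncentrality is 10 × (2/3) × 1.1² × 0.75/(5.76 × (1 − correlation)), with df (6, 81). Power at alpha 0.14 is 0.25, 0.30 and 0.41 for correlations 0.3, 0.5 and 0.7. That is below the adjusted comparison throughout.

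The plan's match in Step 1 needs f = 0.229. The one-arm pattern in Steps 2 to 5 has f = (1.1/2.4) × √2/3 = 0.216, so those figures should be compared with each other and not with 0.44.

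**The case against.** The main-effect reading is an inference. H01 does not say that it averages over visits, no model formula is given, and a two-factor repeated-measures ANOVA often carries an interaction. That is fair, and the power match in Step 1 does not settle it. Still, no hypothesis names the interaction or a post-treatment restriction, and testing H01 as worded includes the baseline visit.

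The contrasts are a stronger point. Rejecting H02 also opens them. All arms receive acupuncture, and naproxen unless refused or contraindicated, so pain may well change over time in every arm. An undiluted needle comparison could therefore be reached even when H01 is not rejected. The power loss shown here belongs to the H01 test, not to every comparison the plan permits. What stands is that none of those comparisons is pre-specified.

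The gain also has two parts. At compound symmetry 0.5, dropping the baseline visit moves power from 0.30 to 0.40, and adjusting for baseline moves it on to 0.53. At AR(1) 0.3 the sequence is 0.39, 0.48, 0.49, so adjustment adds almost nothing there. The second part depends on a correlation that the documents do not give.

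Finally, this is a 30-patient pilot, and the full raw data would let a later analyst adjust for baseline. That limits the consequence. But the plan does state hypotheses, a test and a power, and the better test uses the same data.

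**Conclusion.** The concern holds and should be fixed. As worded, the only between-needle pain hypothesis targets 0.825 points when the post-treatment difference is 1.1. Under the stated assumptions its power at alpha 0.14 is 0.27 to 0.39, against 0.46 to 0.63 for the baseline-adjusted post-treatment comparison. The adjusted test was better in every case checked, though the margin is smaller under AR(1) or when the effect fades by day 7. Both tests remain underpowered. The size of the gain rests on the assumed correlation and effect pattern; the one-quarter dilution rests only on a constant post-treatment difference and none at baseline.

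**What to change.** - **Restate H01 (11.1):** no difference between needle groups in post-treatment DVPRS adjusted for pre-treatment DVPRS.
- **Specify the model (11.6):** fit the three post-treatment scores with baseline DVPRS, needle group, time and group by time as fixed effects and subject as a random effect. Define the H01 test as the 2-df group difference averaged over the three post-treatment times. Other baseline-adjusted longitudinal models would serve, but the omnibus group-by-time test alone would not.
- **Pre-specify the contrasts (11.6):** the three pairwise needle differences in that average, Holm-corrected.
- **Restate the power (11.2, 11.5):** for the restated test, with its assumed correlation.

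H02 may stay as it is. A separate, secondary point in 11.5: age and gender should be fixed covariates or omitted, not random effects.

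The cost is wording in four sections. Baseline DVPRS is already collected, so no new data are needed.
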